7.6.2 Secondary efficacy endpoint

- For the parameters hereafter: Oxford total score on worse eye, OSDI total score, Van Bijsterveld total score, Schirmer test result on worse eye, TBUT total score on worse eye, all ocular dryness symptoms score separately and then globally (total score):
 - For each product, description of the parameter at D0, D35 and D84.
 - For each product, description of the change of the parameter for each time-point (D35-D0 and D84-D0, relative and absolute variation).
 - A mixed ANOVA model (PROC MIXED) for repeated measures will be fitted to raw data, including the factor treatment as fixed (2 levels), time as fixed (3 levels: D0, D35 and D84), and product by time interaction, as well as the patient effect as random. From this model, the contrasts of interest will be built on the adjusted means:
 - To test whether each change from baseline (D35-D0 and D84-D0) differ significantly from 0 by product.
 - To test whether the products differ significantly for each change from baseline (D35-D0 and D84-D0).
 - The underlying assumptions (normality and homoscedasticity) will be checked using Shapiro-Wilk test and graphical representations of the residuals. In case of strong deviation, a non-parametric approach will be performed.
- For OSDI parameter, the different scores will be classified into the following categories:
 - OSDI None: OSDI (0 - <13)
 - OSDI Mild: OSDI (13 - <23)
 - OSDI Moderate: OSDI (23 - <33)
 - OSDI Severe: OSDI (33 - <100)

The parameter will be described at D0, D35 and D84 (with frequency and percentage)

A comparison of the different categories between products at D0, D35 and D84 will be performed, treatments groups will be compared with a Chi2 test.

- For the parameters hereafter: evaluation of performance by the patient, evaluation of performance for the investigator and frequency of use of the product:
 - The parameter will be described at D0, D35 and D84 (with frequency and percentage)
 - A comparison of the parameter between products at D35 and D84 will be performed: for the evaluation of performance by the patient and by the investigator, and for

frequency of use of the products, treatments groups will be compared with a Chi2 test.

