7.1.3 Secondary endpoint(s)

Quantitative data:

Quantitative variables will be summarized by number of patients, mean, median, standard deviation, minimum, and maximum for each time point. Changes from baseline will also be calculated and tabulated for each time-point (D35-D0 and D84-D0).

A mixed ANOVA model (PROC MIXED) for repeated measures will be fitted to raw data, including the factor treatment as fixed (2 levels), time as fixed (3 levels), and product by time interaction, as well as the patient effect as random.

From this model, the contrasts of interest will be built on the adjusted means:

- * to test whether each change from baseline (D35-D0 and D84-D0) differ significantly from 0 by product.
- * to test whether the products differ significantly for each change from baseline (D35-D0 and

D84-D0).

The underlying assumptions (normality and homoscedasticity) will be checked using Shapiro-Wilk test and graphical representations of the residuals. In case of strong deviation, a non-parametric approach will be performed.

Qualitative data:

Categorical variables will be summarized with frequency and percentages for each time point.

For the global performance, treatments groups will be compared with a Chi2 test.

For other qualitative variables, the changes from baseline for each product will be assessed with a Wilcoxon signed-rank test. The comparison between the treatments will be assessed with a Mann-Whitney test for each change from baseline (D35-D0 and D84-D0).

Safety data:

The safety data will be summarised using descriptive statistics by treatment group in the Safety population.

Summary safety assessments include AEs, best-corrected visual acuity, ocular symptoms and the global tolerance assessment by the investigator.

The adverse events will be coded using the MedDRA dictionary. The evaluation of the adverse events only considers the treatment-emergent AEs (TEAEs) with onset date on or after the day of the first study drug instillation.

The ocular TEAEs and the non-ocular TEAEs will be analysed separately.

The number and percentage of patients experiencing at least one AE will be provided by treatment group, by primary SOC and PT, for the following categories of events:

- All AEs
- All TEAEs
- Maximum severity for all events by PT (regardless of causality)
- Treatment-related AEs
- Serious AEs
- AEs that lead to study withdrawal.

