4.1.2 Secondary efficacy endpoints

The secondary efficacy endpoints are described below.

- For the parameters hereafter: Oxford total score on worse eye, OSDI total score, Van Bijsterveld total score, Schirmer test result on worse eye, TBUT total score on worse eye, all ocular dryness symptoms score separately and then globally (total score):
 - For each product, description of the parameter at D0, D35 and D84
 - For each product, description of the change of the parameter for each time-point (D35-D0 and D84-D0)
 - For each product, comparison of the change of the parameter at D35 versus D84
 - Comparison of the change of the parameter between products at D35 and then at D84.
- For the parameters hereafter: OSDI in class, evaluation of performance by the patient, evaluation of performance for the investigator and frequency of use of the product:
 - The parameter will be described at D0, D35 and D84 (with frequency and percentage)
 - A comparison of the parameter between products at D0, D35 and D84 will be performed.

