7.6 Efficacy analyses

7.6.1 Primary Efficacy Endpoint

Primary endpoint derivation

The primary efficacy endpoint is the difference of the change from baseline to day 35 of the Oxford total score in the worse eye between the two patient groups (DM05- Optive®).

The Oxford scale range to 0 (normal) to 15 (greater cornea and conjunctiva staining). An improving of Oxford scale is expected.

The change of the Oxford total score from baseline to day 35 will be derived as below:

Total Oxford score of the examined eye (i.e. worse eye defined at D0) at day 35 - Total Oxford score of the corresponding eye at day 0.

Descriptive analyses:

- Right, middle and left Oxford sub-scores as well as total score will be described on the worse eye at D0 and D35 by treatment groups on both ITT and PP population.
- Change from D0 to D35 of the Oxford total score on the worse eye will be described by treatment groups on both ITT and PP population.

Non-inferiority analysis (main analysis)

In order to demonstrate the non-inferiority of DM05 compared to Optive®, the difference of this change will then be tested between groups in the PP population (DM05 minus Optive®): A two-way analysis of covariance (ANCOVA) model will be constructed using main effects of treatment and baseline score as covariate Adjusted means (least square mean and error standard of the mean) by treatment will be presented as well as an estimate of the difference between adjusted means.

A 95% two-sided confidence interval, based on the ANCOVA model, will be computed for the difference of DM05 minus Optive®:

- If the upper bound of the CI is no higher than 2 points, then the null hypothesis (DM05 is inferior to Optive®) will be rejected.
- Else, if the upper bound is greater than 2, the non-inferiority is not demonstrated.

The result will be presented as follow:

Population	DM05	Optive	Difference DM05 - Optive	95% CI	P non inferiority	P superiority***
Day 0 (baseline) mean (SD)	X1	Y1				
Day 35 mean (SD)	X2	Y2				
Adjusted change between Day 0 and Day 35 - LSM (SEM)	[X2-X1]*	[Y2-Y1]*	[X2-X1] -[Y2- Y1]	[Min - Max**]		

* These values were expected as negative, meaning an improvement of the Oxford score.

** The upper bound indicates the maximal difference of change in disfavor of DM05.

*** In case of demonstration of non- inferiority.

[figure not shown]

Figure 1: interpretation of results —Estimate of the difference and 95% CI are presented for 4 situations.

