The p value of non-inferiority will be expressed taking on board the predefined margin of non-inferiority.

The MIXED procedure (SAS®) will be used.

SAS code:

```
proc mixed data=XX order=data;
  where PP = 1 ;
  class TT;
  model EVOL = BASELINE TT /* Other covariates can be added here */;
  lsmeans TT / diff;
run;
```

In case of conclusion of non-inferiority of DM05 compared to Optive®, the superiority of DM05 compared to Optive® will then be tested on both ITT and PP population in the same way as described above for the non-inferiority:

- If the upper bound of the CI is no higher than 0 points, then the null hypothesis (DM05 is not superior to Optive®) will be rejected. meaning that DM05 is superior to Optive.
- Else, if the upper bound is greater than 0, the superiority is not demonstrated.

Sensitivity analysis

1. If a statistically difference will appear between the 2 groups at baseline on age and/or sex, a sensitivity analysis will be conducted on PP population with the same used for main analysis including this or these factor(s).

The same analysis will be performed on ITT population with imputation of values in case of missing data with LOCF technique (baseline value or value in case of withdrawal).

The result will be presented in the same way as the main analysis.

2. Centre + treatment + interaction treatment*centre will be tested on the primary end point. If p value is lower than 0.10, it is declared that there is an interaction between treatment and centre. In this situation, a sensitivity analysis will be conducted on PP population with the same factors used for main analysis including this factor.

The same analysis will be performed on ITT population with imputation of values in case of missing data with LOCF technique (baseline value or value in case of withdrawal)

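### Product comparisons on 13 quantitative secondary outcomes are unadjusted change contrasts, although D0 is collected for each and the primary model adjusts for it; baseline adjustment would gain precision at little cost.

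*SAP*

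**What the plan says.** SAP 7.6.2 covers Oxford, OSDI, Van Bijsterveld, Schirmer, TBUT, the seven symptom scales and the symptom total, which makes 13 outcomes. The fixed effects are treatment, "time as fixed (3 levels: D0, D35 and D84), and product by time interaction, as well as the patient effect as random". Protocol 7.1.3 has the same model: "A mixed ANOVA model (PROC MIXED) for repeated measures will be fitted to raw data". No baseline covariate is listed, and the arms are not constrained to share a D0 mean.

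Two sets of contrasts come from this model:

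- Between products: "Comparison of the change of the parameter between products at D35 and then at D84" (SAP 4.1.2).
- Within product: "To test whether each change from baseline (D35-D0 and D84-D0) differ significantly from 0 by product" (SAP 7.6.2).

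The primary analysis of the Oxford change at D35 is built differently: "A two-way analysis of covariance (ANCOVA) model will be constructed using main effects of treatment and baseline score as covariate", with code "model EVOL = BASELINE TT" (SAP 7.6.1). Superiority "will then be tested on both ITT and PP population in the same way as described above for the non-inferiority", so it also rests on the ANCOVA.

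The schedules in protocol 6.1.5 and SAP 3.5 collect all 13 outcomes at D0. The adjusted means named in SAP 7.6.2 are least-squares means of the model described there. They imply no adjustment for D0.

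**The concern.** There are two consequences.

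**Precision.** With D0 as a free response in both arms, the product-by-time contrast does not use the correlation between D0 and follow-up as a covariate would. The secondary objective compares the products on other signs and symptoms at D35 and D84, in a trial sized only for the primary endpoint. Precision is given up there although the data to recover it are already collected.

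**Calibration.** A single random patient effect, with nothing further specified, implies the same variance at each visit and the same correlation for each pair of visits. The visits are 35 and 49 days apart. If correlation declines with time, one pooled error term cannot fit both the D35 and the D84 contrast. This affects the product comparisons and the within-product tests of change. The planned check, "The underlying assumptions (normality and homoscedasticity) will be checked using Shapiro-Wilk test and graphical representations of the residuals", is not aimed at unequal correlations.

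**Working it through.** **Inputs from the documents.** 34 analysed per arm, SD 2.5, margin 2, 15% drop-out and 80 randomised (protocol 7.2, SAP 6.1). Entry ranges are in protocol 6.3.1. Two-sided 5% is in SAP 6.2.

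**Inputs assumed.** All correlations; 2.5 as a visit SD; an Oxford D0 SD of 1.7, because integers 4–9 taken as uniform have SD √(35/12) = 1.71.

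**1. The plan's own figure.** SE = 2.5 × √(2/34) = 0.606 and 2/0.606 = 3.30. This gives 90% power (0.902 by noncentral t), and 68/0.85 = 80. The primary sample size reproduces. The documents state no size or power for the secondary contrasts.

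**2. What the model estimates.** The random-patient model was fitted to one simulated complete dataset with a D0 imbalance built in. Its contrasts were −0.1033 and −0.1665, identical to the raw differences in mean change. ANCOVA on the same data gave +0.007 and −0.070, with SE 0.166 and 0.180 against 0.201.

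**3. Precision, equal visit SDs.** Per arm, the variance is 2(1−r)σ² for change and (1−r²)σ² for the adjusted contrast. The SE ratio is therefore √(2/(1+r)).

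| r | Plan SE | Adjusted SE | Ratio | Plan power where adjusted = 80% |
|---|---|---|---|---|
| 0.3 | 0.717 | 0.578 | 1.240 | 63% |
| 0.5 | 0.606 | 0.525 | 1.155 | 70% |
| 0.7 | 0.470 | 0.433 | 1.085 | 75% |

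With 40 per arm, 6 of them having D0 only (missing at random), the ratios are 1.207, 1.133 and 1.072.

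**4. Outcomes restricted at entry.** If a normal baseline loses its lower tail and keeps a fraction V of its variance, the ratio is √(1 + V(1−r)/(1+r)). Cutting 20% leaves V = 0.583, and cutting 50% leaves V = 0.363.

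| r | Ratio, 20% cut | Ratio, 50% cut |
|---|---|---|
| 0.3 | 1.146 | 1.093 |
| 0.5 | 1.093 | 1.059 |
| 0.7 | 1.050 | 1.032 |

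This illustrates OSDI, which must be at least 18 at entry. The cut fractions are assumed.

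**5. Oxford.** The general ratio is √(1 + (s₀ − r·s₁)² / (s₁²(1−r²))). With s₀ = 1.7 and s₁ = 2.5 it is 1.076, 1.021 and 1.000. If 2.5 is instead the SD of change, s₁ becomes 2.41, 2.87 and 3.38, and the ratios are 1.09, 1.01 and 1.04.

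**6. Type I error.** With equal SDs the pooled error term estimates σ²(1 − r̄), where r̄ is the mean of the three correlations. The contrast needs σ²(1 − r₀ₖ). So type I error ≈ 2[1 − Φ(1.96·√((1−r̄)/(1−r₀ₖ)))]. For 0.5/0.3/0.7 at D84, r̄ = 0.5 and 0.7/0.5 = 1.4, which gives 9.8%. Simulation (20,000 trials, 34 per arm, complete data) agrees:

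| Correlations D0–D35 / D0–D84 / D35–D84 | D35, formula | D35, simulated | D84, formula | D84, simulated |
|---|---|---|---|---|
| 0.5/0.45/0.55 | 5.0% | 4.8% | 6.2% | 6.0% |
| 0.5/0.4/0.6 | 5.0% | 5.3% | 7.4% | 7.2% |
| 0.5/0.3/0.5 | 3.7% | 3.6% | 7.8% | 7.7% |
| 0.5/0.3/0.7 | 5.0% | 5.1% | 9.8% | 9.6% |

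Within-product D84 tests in the same order gave 6.1%, 7.4%, 7.5% and 10.0%. With D0 SD 1.7, product contrasts at D84 run from about 5% to 8.5–9.0%, and at D35 from about 3.3% to 4.6%. Baseline-adjusted contrasts stayed at about 5% throughout. With equal SDs and a common correlation the plan's contrast also holds 5%.

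**The case against.** The planned contrast is valid: it is pre-specified and unbiased under randomisation. A reader might infer that the secondary comparisons are biased. They are not. A chance D0 imbalance enters a single trial's estimate but averages out.

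A reader might also apply the 24/15/8% loss to all 13 outcomes. The entry criteria do not support that. OSDI is cut directly, Oxford is held to 4–9, and Schirmer or TBUT is restricted through an either/or criterion. The equal-SD figures fit best where entry sets no limit: Van Bijsterveld, the seven symptoms and their total.

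It is fair to say that SAP 7.6.2 gives no code, residual structure or degrees-of-freedom method. A random intercept with independent residuals is the natural reading, but the text does not exclude a richer structure. It is also fair that the error-rate result is conditional, since the documents contain no correlations. The plan cannot be said to have an inflated error rate, only to be exposed to one if correlation declines with time.

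Finally, no formal decision rests on these tests. Protocol 7.4 sets pass/fail on the primary endpoint alone. Oxford at D35 will receive a second product p-value from the secondary model, but the ANCOVA is labelled the main analysis, so this is only a reporting matter.

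What stands is that a stated secondary objective is analysed less efficiently than the collected data allow, by a method the same SAP improves on for its primary endpoint.

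**Conclusion.** The point holds as a cheap improvement to the secondary analyses, not as an error in the primary inference. Non-inferiority and superiority are both unaffected.

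- **Precision:** the SE is 24%, 15% and 8% larger at r = 0.3, 0.5 and 0.7 for outcomes not restricted at entry, assuming equal visit SDs. This is an upper case for OSDI (about 9–15%, 6–9% and 3–5% under the assumed truncation) and probably for Schirmer and TBUT. For Oxford the loss is about 8%, 2% and 0%. It stays small on either reading of the 2.5, which the documents do not identify as a visit SD or an SD of change.
- **Error rate:** under the natural reading of the model, and only if correlation falls with time, D84 type I error is about 6–8% under mild to moderate decay with equal SDs. It reaches about 9–10% in the most extreme pattern tried. D35 ranges from conservative to nominal, about 3–5%.

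The direction of the precision result is firm for equal SDs and any correlation below 1. The sizes depend on the stated assumptions.

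**What to change.** Amend SAP 7.6.2, and record the departure from protocol 7.1.3 in SAP 5.3, which now lists no changes.

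1. **Between-product contrasts.** Preferably use a three-visit model with one D0 mean common to both arms and unstructured covariance (REPEATED visit / SUBJECT=patient TYPE=UN) in place of the random patient effect, with Kenward-Roger degrees of freedom. This keeps ITT patients who have D0 only. Alternatively, model the D35 and D84 changes with treatment, visit, treatment × visit, baseline and baseline × visit, with TYPE=UN and the same degrees of freedom.
2. **Within-product tests.** Use a three-visit TYPE=UN model or a paired analysis. Do not use baseline-adjusted least-squares means: in simulation with equal SDs their type I error was 8.1–8.3%, 6.9–7.0% and 5.7–5.8% at r = 0.3, 0.5 and 0.7.

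The cost is SAP text and different PROC MIXED calls, with no new data. The covariance parameters rise from 2 to 6 (three-visit model) or 3 (change model). The change model drops D0-only patients. Under random drop-out this costs the adjusted contrast nothing: its SE is 0.578, 0.525 and 0.433 with or without them.

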6.1.4.1.2 Ocular Surface Disease Index (OSDI)

The OSDI is assessed on a scale from 0 to 100, with higher scores representing greater disability. The patients will be asked the following 12 questions:

Have you experienced any of the following during the last week?	All of the time	Most of the time	Half of the time	Some of the time	None of the time
1. Eyes that are sensitive to light.	4	3	2	1	0
2. Eyes that feel gritty?	4	3	2	1	0
3. Painful or sore eyes?	4	3	2	1	0
4. Blurred vision?	4	3	2	1	0
5. Poor vision?	4	3	2	1	0
Subtotal score for answers 1 to 5					A

Have problems with your eyes limited you in performing any of the following during the last week ?	All of the time	Most of the time	Half of the time	Some of the time	None of the time	NA
6. Reading?	4	3	2	1	0	NA
7. Driving at night?	4	3	2	1	0	NA
8. Working with a computer or bank machine (ATM)?	4	3	2	1	0	NA
9. Watching TV?	4	3	2	1	0	NA
Subtotal score for answers 6 to 9					B	

Have your eyes felt uncomfortable in any of the following situations during the last week ?	All of the time	Most of the time	Half of the time	Some of the time	None of the time	NA
10. Windy condition?	4	3	2	1	0	NA
11. Places or areas with low humidity (very dry)?	4	3	2	1	0	NA
12. Areas that are air conditioned	4	3	2	1	0	NA
Subtotal score for answers 10 to 12					C	

Add subtotals A, B and C to obtain D (D=sum of scores for all questions answered)	D
--	----------

Total number of questions answered (do not include questions answered NA)	E
--	----------

OSDI is calculated according to the following formula: $OSDI = D \times 25 / E$

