4.3 Derived variables

Source data	Derivation rule	Label	Format
Date of last use of study product, date of D0 visit	TRT_DUR_D=Date of last use of study product – date of D0 visit +1	Treatment duration in days	Numeric
Date of end of study, date of selection visit	STUDY_DUR_D=Date of end of study – date of selection visit +1	Study duration in days	Numeric
OSDI total score	IF 0<=OSDI total score < 13 THEN OSDI_CL_D=1 IF 13<= OSDI total score < 23 THEN OSDI_CL_D=2 IF 23<= OSDI total score < 33 THEN OSDI_CL_D=3 IF 33<= OSDI total score < 100 THEN OSDI_CL_D=4	OSDI score in class	1 = "OSDI none" 2 = "OSDI Mild" 3 = "OSDI moderate" 4 = "OSDI severe"
Total Oxford score of the examined eye (i.e. worse eye defined at D0) at day 0, Total Oxford score of the corresponding eye at day 35 (i.e. day 84)	EVOL_OX_D0D35 (i.e. D84) = Total Oxford score of the examined eye (i.e. worse eye defined at D0) at day 35 (i.e. day 84) - Total Oxford score of the corresponding eye at day 0	Change of the Oxford total score from baseline to day 35 (i.e. day 84)	Numeric
Same derivation rule as above for changes on OSDI total score, Van Bijsterveld total score, Schirmer test result, TBUT total score, all ocular dryness symptoms score from D0 to D35 and from D0 to D84.			

Total Oxford score of the examined eye (i.e. worse eye defined at D0) at day 0, Total Oxford score of the corresponding eye at day 35 (i.e. day 84)	EVOL_OXREL_D0D35 (i.e. D84) = (Total Oxford score of the examined eye (i.e. worse eye defined at D0) at day 35 (i.e. day 84) - Total Oxford score of the corresponding eye at day 0) / Total Oxford score of the corresponding eye at day 0	Relative change of the Oxford total score from baseline to day 35 (i.e. day 84) in percentage	Numeric
Same derivation rule as above for changes (relative variation) on OSDI total score, Van Bijsterveld total score, Schirmer test result, TBUT total score, all ocular dryness symptoms score from D0 to D35 and from D0 to D84.			
Adverse Event	IF at least one adverse event is reported for the patient, ALO_AE=1 ELSE, ALO_AE=0	At least one AE	0 = "No" 1 = "Yes"
Same derivation rule as above for at least one TEAE, at least one severe AE, at least one AE related to the treatment, at least one SAE, at least one AE that lead to study withdrawal			

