6.2 Generalities for statistical analyses

Continuous variables will be summarized by number of non-missing observations, mean, standard deviation, minimum, median, maximum.

Categorical data will be summarized by frequency and percentage of patients in each category. Percentages will be based on non-missing observations.

All statistical tests will be 2-tailed with a Type I error of 0.05 unless otherwise stated.

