8.4 Examples of tables, listings and figures

8.4.1 Quantitative variables:

Table xx: Description of quantitative variables

		Group A N=xxx	Group B N=xxx	Total N=xxx	p-value
Variable 1	N	x	x	x	
	Missing	x	x	x	
	Mean \pm SD	xx.xx \pm xx.xx	xx.xx \pm xx.xx	xx.xx \pm xx.xx	
	Median	xx.xx	xx.xx	xx.xx	
	Q1 ; Q3	xx.xx ; xx.xx	xx.xx ; xx.xx	xx.xx ; xx.xx	
	Min. ; Max.	xx.xx ; xx.xx	xx.xx ; xx.xx	xx.xx ; xx.xx	
Variable 2	N	x	x	x	
	Missing	x	x	x	
	Mean \pm SD	xx.xx \pm xx.xx	xx.xx \pm xx.xx	xx.xx \pm xx.xx	
	Median	xx.xx	xx.xx	xx.xx	
	Q1 ; Q3	xx.xx ; xx.xx	xx.xx ; xx.xx	xx.xx ; xx.xx	
	Min. ; Max.	xx.xx ; xx.xx	xx.xx ; xx.xx	xx.xx ; xx.xx	

95% Confidence Intervals might be presented in the tables.

8.4.2 Qualitative variables:

Table xx: Description of qualitative variables

		Group A N=xxx	Group B N=xxx	Total N=xxx	p-value
Variable 1	N	x	x	x	x
	Missing	x	x	x	x
	Modality 1	xx (xx.x%)	xx (xx.x%)	xx (xx.x%)	xx (xx.x%)
	Modality 2	xx (xx.x%)	xx (xx.x%)	xx (xx.x%)	xx (xx.x%)
Variable 2	N	x	x	x	x
	Missing	x	x	x	x
	Modality 1	xx (xx.x%)	xx (xx.x%)	xx (xx.x%)	xx (xx.x%)
	Modality 2	xx (xx.x%)	xx (xx.x%)	xx (xx.x%)	xx (xx.x%)

95% Confidence Intervals might be presented in the tables.

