11 APPENDICES

11.1 Appendix 1: Level of validation for analyses programming

This chapter documents the validation of the statistical analysis programs. The level of validation is defined with reference to the procedure “Programming of the statistical analysis”.

All the analyses and programs have a default validation level “Basic + NC”.

Analysis below have a CR validation level:

Analyses	Validation level	Programs
Primary efficacy endpoint (section 7.6.1)	CR	ANA_PRINC

Key:

Basic = Corresponds to the self-check of the programming by any person who is required to program, as well as the checking of derived variables (see self-check frame)

NC (non-critical) = The tables, listings and figures compiled in a single document shall be verified by one qualified person other than the program developer with the support of the CRF and SAP for the study.

CR (critical) = A double programming and a comparison of the results should be performed by one qualified person other than the program developer.

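### Minor, secondary output only: the OSDI class rule stops below 100, so the attainable maximum score has no class

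*SAP*

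**What the plan says.** **OSDI scale.** Protocol 6.1.4.1.2: "The OSDI is assessed on a scale from 0 to 100, with higher scores representing greater disability". Each of 12 items scores 0 to 4, and the total is 25 times the sum of the answered items (D) divided by the number answered (E). Items 1 to 5 have no not-applicable option.

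**OSDI classes.** SAP 4.3 derives the class with four IF statements and no ELSE. The last is "IF 33<= OSDI total score < 100 THEN OSDI_CL_D=4". SAP 7.6.2 repeats the bound in words: "OSDI Severe: OSDI (33 - <100". The classes are tabulated and compared between products with Chi2 at D0, D35 and D84.

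**Tabulation and checking.** SAP 6.2: "Percentages will be based on non-missing observations". The example shell in SAP 8.4.2, "Table xx: Description of qualitative variables", has a row for missing values. Under SAP Appendix 1 only the primary endpoint is double programmed. Other output is "verified by one qualified person other than the program developer with the support of the CRF and SAP for the study".

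**Performance ratings.** Protocol 6.1.4.1.7 gives patient and investigator a four-level ordered scale, from very satisfactory to unsatisfactory. Protocol 7.1.3 plans a Chi2 test for it. SAP 7.6.2 agrees. It plans the comparison "at D35 and D84 will be performed: for the evaluation of performance by the patient and by the investigator", and says that for these ratings and for "frequency of use of the products, treatments groups will be compared with a Chi2 test". SAP 4.1.2 lists a D0 comparison as well, although the schedule in SAP 3.5 collects no rating at D0.

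**The concern.** The two passages that define the severe class leave out the upper end of the scale, and no other class takes it. Because both carry the same bound, neither corrects the other. A program that follows the SAP faithfully leaves the class empty for a patient with the worst possible score, and a check of the table against the SAP would not show this as a programming error.

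At stake is the accuracy of one secondary table and its Chi2 test, if such a patient occurs. The patient with the highest symptom burden would then be the one left out of the severe count.

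**Working it through.** The plan gives no figure of its own on this point, so there is none to reproduce.

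**Is 100 attainable?** If every answered item scores 4, then D = 4E and the score is 25 × 4E / E = 100 for any E. With all 12 items, 25 × 48 / 12 = 100. The inclusion criterion (Protocol 6.3.1) is OSDI of at least 18 with no upper limit, so 100 is eligible at baseline and possible at D35 and D84.

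**Is it the only gap?** E runs from 5 to 12, because items 1 to 5 must be answered. The number of possible (D, E) pairs is the sum of (4E + 1) = 4 × 68 + 8 = 280, giving 185 distinct scores. Passed through the rule in SAP 4.3, every score except 100 falls in exactly one class. The score 100 arises once for each E, at D = 4E.

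**Size, if one patient scores 100.** Let an arm have n patients, s of them truly severe including this one. The percentage should be s/n. If the unclassified patient leaves numerator and denominator, it becomes (s − 1)/(n − 1). The loss is s/n − (s − 1)/(n − 1) = (n − s) / [n(n − 1)].

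The arm sizes come from the plan: 40 per arm randomised (Protocol 6.3.6) and 34 per arm evaluable (SAP 6.1). The documents give no expected number of severe patients, so s is assumed over a range.

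| n per arm | s = 1 | about half severe | about three quarters severe |
|---|---|---|---|
| 40 | 39/1560 = 2.50 points | s = 20: 20/1560 = 1.28 | s = 30: 10/1560 = 0.64 |
| 34 | 33/1122 = 2.94 points | s = 17: 17/1122 = 1.52 | s = 25: 9/1122 = 0.80 |

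The loss shrinks to zero if the whole arm is severe.

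**Optional remark: Chi2 on ordered ratings.** The documents give no expected rating distribution, so these figures are illustrative. They come from 40,000 simulated tables per scenario at 34 and 40 per arm, two-sided 5%, comparing Pearson Chi2 with a tie-corrected Mann-Whitney test under proportional-odds shifts.

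| Mann-Whitney power minus Chi2 power (points) | OR 1.5 | OR 2 | OR 3 |
|---|---|---|---|
| four filled levels | 4.7 to 6.2 | 11.7 to 13.9 | 17.0 to 19.3 |
| three filled levels | 2.6 to 3.4 | 6.9 to 8.2 | 9.5 to 11.0 |
| two filled levels | 0 to −1.2 | 0 to −2.0 | 0 to −2.0 |

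One example: with 25/45/20/10% in one arm, OR 2 and 34 per arm, power is 20.5% for Chi2 and 32.8% for Mann-Whitney, so neither is well powered. With no difference and three or four levels, Chi2 rejects in 4.2 to 5.2% and Mann-Whitney in 4.8 to 5.2%. Where the arms differ but not by a one-way shift, the advantage reverses: Chi2 has 44 to 66% power and Mann-Whitney 5 to 6%.

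**The case against.** **On the OSDI class.** A score of 100 needs the worst answer on every answered item, and nothing in the documents suggests that anyone will give it. The Missing row belongs to an example shell, and no passage says how an unclassified score is handled. Appendix 1 also requires a self-check of derived variables, so someone may notice a total of 100 beside an empty class. OSDI class is not a named protocol endpoint, and OSDI total score is tabulated and modelled separately. All of this stands and limits the weight of the point. It does not make the rule correct, because the stated derivation still fails for an attainable score.

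A reader might infer that the trial will report its most severe patients as missing data. The documents do not support that. It requires a patient at exactly 100, and the handling as missing is an inference, though a likely one.

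**On the performance ratings.** A reader might also infer that Chi2 is the wrong test. It is not. It is valid, and protocol and SAP agree on it. A rank test gains power only under an assumed pattern of difference and loses heavily under others. Preferring one is a choice with a trade-off, so it stays a remark here. The Chi2 on OSDI classes is not challenged either, because OSDI total score has its own mixed model.

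**Conclusion.** The OSDI class rule is wrong as written for one score, 100, in both SAP 4.3 and SAP 7.6.2. The consequence is conditional. One patient at 100 would lower that arm's severe percentage by about 0.6 to 2.9 points. This assumes 34 or 40 patients per arm, between one patient and about three quarters of the arm severe, and an unclassified patient treated as missing. If nobody scores 100, nothing changes. The effect is confined to the OSDI class table and its Chi2 comparison; the OSDI total-score mixed model and the Oxford non-inferiority analysis do not use the class. The order-blind test on the performance ratings is an optional efficiency matter and does not carry the point.

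**What to change.** **Needed.** Change the top class to 33 <= OSDI <= 100 in SAP 4.3 and SAP 7.6.2. This corrects one bound in two places before database lock, with no new data and no drawback.

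**Optional.** In SAP 7.6.2, add a Wilcoxon-Mann-Whitney or row-mean-score test of the patient and investigator ratings at D35 and D84 as supportive to the Chi2, and record the addition in SAP 5.3, which now lists no change from the protocol. The cost is more unadjusted p-values: 2 raters × 2 visits × 2 populations = 8 now, and 16 with a second test, while SAP 6.5 plans no multiplicity control. Patients are not blinded (Protocol 6.1.2), so a more sensitive test of their rating is also more sensitive to expectation.

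**If SAP 4.1.2 is aligned at the same time.** Split its comparison sentence; do not simply delete D0. Keep D0, D35 and D84 for OSDI class, as SAP 7.6.2 plans, and limit the performance ratings to D35 and D84. The sentence also covers frequency of use, which SAP 7.6.2 compares only at D35 and D84. Remove the D0 descriptions of the performance ratings from SAP 7.6.2 and from the planned tables in SAP 9.1.
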